6.2.1.2 Safety Endpoints

In general, all available data from subjects who have prematurely discontinued from the study will be used for analysis. For AEs with missing information for the intensity and causality, it will be represented as a missing category.

6.2.2 Missing or Partial Date

In all listings, missing or incomplete dates will be left as they have been recorded. However, for calculation / sorting / assignation based on dates, the following methods will be used:

- (1) If the onset date of an AE/concomitant medication is missing / incomplete, it is assumed to have occurred during the study treatment phase (i.e. a treatment-emergent adverse event (TEAE) for AEs) except if the partial onset date or stop date indicates differently.
- (2) A missing / incomplete date of medical history or disease diagnosis will be assumed to have occurred before any study treatment. For calculation purposes, if only the year is available, then the first day of January will be used to impute, if only the day is missing then the first day of the month will be used to impute.
- (3) An AE could be assigned to several possible treatment cycles according to its partial onset date and stop date. If only the AE start day is missing, then the AE will be assigned to that treatment cycle that includes the first day of that month. If the AE start date has a

missing month, then January will be used. An AE with missing start date will be assigned to each treatment cycle before its end date. The Analysis Data Model programming specifications will outline the rules in more detail. During the study, examples of date imputations will be shared with the team to ensure AE assignment to treatment cycles are in agreement with the team.

- (4) In calculations with date of the first IMP administration, if missing, the date of randomisation will be used.

7 STATISTICAL METHODS

7.1 General Principles

All data processing, summarisation and analyses will be performed using the SAS Environment / Version 9.4 (or later) of the SAS[®] statistical software package.

All data collected during the study will be presented in listings without any imputation by treatment group, subject, assessment and visit (where applicable), unless otherwise specified.

Data will be presented in summary tables by treatment group (as described below), assessment and visit (where applicable).

Overall, the analysis strategy is to evaluate efficacy and safety data from the initial DBPC Cycle and to evaluate efficacy and safety over repeated Dysport treatments, using analyses by Dysport Cycle (Dysport Cycle 1, 2...etc.), as illustrated in schematic diagram later in this section. In general, tables associated with the DBPC Cycle will be separate from the tables assessing repeat treatment with Dysport which are presented by Dysport Cycle:

- During analysis of the DBPC (DBPC cycle), data will be displayed using the following treatment group labels, in the order presented:
 - Placebo
 - Dysport 600 U
 - Dysport 800 U
 - All Dysport
- During analysis by Dysport Cycle, data will be displayed by number of Dysport treatments (see diagram below) using the following treatment group labels:
 - Dysport Cycle 1
 - Dysport 600U
 - Dysport 800U
 - All Dysport
 - Dysport Cycle 2
 - Dysport 600U
 - Dysport 800U
 - All Dysport
 - Dysport Cycle X

Statistical Analysis Plan

Version: Final v1.0
September-2018
Ipsen Protocol No. D-FR-52120-223
000000146513

[figure not shown]
Date of Issue: 21-
Covance Study ID:

- Dysport 600U
- Dysport 800U
- All Dysport

Analysis of Dysport Cycle 1 will therefore include (see diagram below):

- Data from subjects who received a Dysport treatment after having initially received placebo as their first study treatment on Day 1 i.e. will only use data from their first Dysport treatment,
- Data from subjects who received Dysport as their first study treatment on Day 1

Schematic diagram summarising concept of Dysport Cycles:

Descriptive summary statistics for continuous variables will include the number of subjects (n), mean, standard deviation (SD), median, minimum and maximum.

Descriptive summary statistics for categorical variables will include frequency counts and percentages [n (%)]. The denominator for percentage calculations will be the number of subjects in the analysis population for the designated treatment cycles. Unless stated otherwise in the table shells (e.g. for the TEAE of MS relapse, the denominator only relates to the number of MS subjects),

Dates will be displayed as DDMMMYYYY.

Overall, in the statistical tables the category “Missing” will be presented if the number missing is > zero for at least one treatment group.

Unless otherwise specified, the eCRF recorded strata (i.e. the correct strata) will be analysed for all used in all the data displays.

7.2 Subject Disposition and Data Sets Analysed

Subjects randomised will be summarised by country and site, and also summarised by aetiology of NDO (SCI or MS), and previous BTX-A usage (BTX-A naïve vs. BTX-A non-naïve in the bladder) for the Randomised population.

The number of subjects screened but not randomised (screen failures) will be tabulated by country. The reasons for screen failures will be listed.

The randomisation details will be displayed in a listing for the Randomised population.

The number and percentages of enrolled subjects included in analysis populations (Randomised, Safety, mITT, PP and urodynamic) will be summarised by treatment group and overall. The reason for subject exclusion from each of the populations will be tabulated and listed.

In addition, the number and percentage of subjects who completed the study, prematurely discontinued the study with primary reasons will be tabulated by treatment group in the Randomised population. The number of subjects entering, prematurely withdrawing with primary reasons will be tabulated by treatment group in the Randomised population for the DBPC Cycle and by Dysport Cycle. Subject disposition data, including retreatments after the first IMP administration, and study discontinuation will be listed.

7.3 Protocol Deviations

All protocol deviations will be listed for the Randomised population.

The protocol deviations, including defining those leading to exclusion from the PP population, will be identified before data are unblinded.

7.4 Demographics and Other Baseline Characteristics

Demographic and baseline characteristics will be listed and summarised for the mITT population.

Standard descriptive statistics including 95% confidence interval (CI) will be presented for the continuous variables of:

- Age (years)
- Weight (kg);
- Height (cm);
- Body mass index (BMI) (kg/m^2) calculated as $[\text{weight}(\text{kg})/(\text{height}(\text{cm})/100)^2]$

The total counts and percentages of subjects will be presented for the categorical variables of:

- Age groups [≥ 18 and ≤ 40 , >40 and ≤ 65 , > 65 years (further categorising to >65 and ≤ 75 , and >75 years))
- Sex (Male, Female);
- Race (Asian, Black or African American, White, Native Hawaiian or Other Pacific Islander, American Indian or Alaska Native and Other);
- Ethnicity (Hispanic/Latino, Not Hispanic/Latino);
- Stratification variables:

- aetiology of NDO (SCI, MS)
- previous intradetrusor BTX-A usage (BTX-A bladder naïve, BTX-A bladder non-naïve).
- Other baseline characteristics:
 - prior NDO oral medications (Yes, No)
 - concomitant NDO oral medications at time of first IMP administration (Yes, No)
 - prior treatment of anticholinergics (Yes, No)
 - concomitant treatment of anticholinergics at time of first IMP administration (Yes, No)
 - prior beta-3 agonists (Yes, No)
 - concomitant beta-3 agonists at time of first IMP administration (Yes, No)
 - daily CIC frequency at baseline
 - history of UTI in the 6 months prior to study (Yes, No)
 - using a wheelchair regularly in subjects with MS (Yes, No)

No formal tests of statistical significance will be performed on the demographic and baseline data. Other baseline data not only measured at screening will be summarised by treatment group with the post-baseline measurements.

The demographics and baseline characteristics data will also be summarised by aetiology of NDO (SCI, MS) for the mITT population.

Pregnancy test will be listed only.

7.4.1 UTI Prior to First IMP Administration

The counts and percentages of the following categories will be summarised for the mITT population:

- Overall subjects with UTI prior to first IMP administration
- Subjects with a medical history of UTI
- Subjects with a medical history of UTI within 6 months prior to screening
- Subjects with a recorded AE of UTI between informed consent and first IMP administration

7.4.2 Medical History

Medical History (significant medical or surgical history, NDO medical history for SCI and MS subjects) will be coded by Sponsor using the Medical Dictionary for Regulatory Activities [MedDRA v21.0 (March 2018); latest version if updated during the study). All medical history will be listed, and the number and percentage of subjects with any medical history will be summarised for the mITT population by system organ class (SOC) and preferred term (PT) for each treatment group and overall.

NDO Medical History will be summarised by aetiology of NDO (SCI, MS). Duration of NDO will be calculated as (informed consent date - date of development of NDO symptoms)*12/365.25 and reported as whole months, and presented using standard descriptive statistics.

For SCI history, percentage of neurological level of stable SCI, cause of stable SCI, American Spinal Injury Association (ASIA) Grade and neurological syndrome will be summarised. Duration of SCI will be calculated as (date of the first IMP administration - date of stable SCI)*12/365.25 and reported as whole months, and presented using standard descriptive statistics.

For MS history, the percentage of level of mobility, classification of MS will be summarised. Duration of MS will be calculated as (date of the first IMP administration - date of initial diagnosis)*12/365.25 and reported as whole months, and presented using standard descriptive statistics. Duration of onset of symptoms will be calculated as (date of the first IMP administration - date of onset of symptoms)*12/365.25 and reported as whole months, and presented using standard descriptive statistics.

7.4.3 Prior and Concomitant Medications

Medications received prior to or concomitantly with treatment will be coded by Sponsor using World Health Organisation Drug Dictionary (WHO Drug Dictionary; Version B2-BDE March 2016 or a later version if updated during the study), and will be summarised by treatment group and overall with the number and percentage of subjects, by therapeutic class (the Anatomic Therapeutic Chemical [ATC] Classification codes) and preferred term. The concomitant medications and therapies will be summarised separately for the DBPC Cycle and by Dysport Cycle (Dysport Cycle 1, 2, etc).

Prior medications and concomitant medications are defined as follows:

Prior medications/non-drug therapies are those taken within 30 days prior to screening with a stop date prior to the date of the first IMP administration. Prior medications or therapies for NDO are those with both start date and stop date prior to the date of the first IMP administration.

Concomitant medications are those with a start date on or after the date of the first IMP administration, or those with a start date before the date of the first IMP administration and a stop date on or after the date of the first IMP administration (or ongoing).

Prior medications and concomitant medications will be listed together and summarised separately for the mITT population. Similarly, this will be listed and summarised for the prior and concomitant medications for NDO, and for prophylactic antibiotic for initial treatment, retreatments and urodynamic assessments.

Concomitant Surgical Procedures will be summarised by SOC and PT for the mITT population.

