Screening period will last for up to 30 days, but can be extended in certain circumstances to obtain an appropriately and fully completed bladder diary or to obtain a valid bladder diary. Furthermore, where a urinary tract infection (UTI) occurs after completion of the bladder diary and impacts the ability to perform urodynamics, the time to Screening Visit 2 can be extended until the UTI is resolved. During the screening period, informed consent will be obtained and eligibility for study participation will be assessed. Subjects will complete a 7-day bladder diary, urodynamic assessment, patient-reported outcome questionnaires and have blood and urine samples taken.

Randomisation/treatment

The Treatment Visit (Day 1) should occur up to 14 days after the screening period, but can be extended until the UTI is resolved (where a UTI has occurred and impacts the ability to perform IMP administration). At the Treatment 1 visit on Day 1, subjects who meet all the eligibility criteria will be randomised (in a 2:2:1:1 ratio) to one of four treatment sequences:

Sequence	Subjects	1 st Treatment in DBPC Cycle	Subsequent retreatment(s) in Dysport Cycles (Dysport Cycle 1, Dysport Cycle 2, etc)
1	110 subjects	Dysport 600 U	Dysport 600 U
2	110 subjects	Dysport 800 U	Dysport 800 U
3	55 subjects	Placebo	Dysport 600 U
4	55 subjects	Placebo	Dysport 800 U

During the analysis of DBPC cycle, the two placebo containing sequences will be pooled into a single arm.

Randomisation will be stratified by;

- Aetiology of NDO (SCI or MS)
- Previous intradetrusor botulinum toxin type A (BTX-A) usage (BTX-A naïve vs. BTX-A non-naïve).

Follow-up (after IMP administration in DBPC cycle):

- Week 1 (Day 8) (telephone)
- Week 2 (Day 15) (clinic visit)
- Week 4 (Day 29) (telephone)
- Week 6 (Day 43) (clinic visit; primary timepoint)
- Week 12 (Day 85) (clinic visit; the retreatment could be requested by subject from this visit)
- Every 12 weeks (telephone visits; until retreatment received or end of study (EOS) at Weeks 104 to 116).

Statistical Analysis Plan

Version: Final v1.0

September-2018

Ipsen Protocol No. D-FR-52120-223

000000146513

Date of Issue: 21-

Covance Study ID:

Details of the procedures performed at each visit following the first treatment are shown in the schedule of assessments, [Appendix V](#).

Retreatment assessment

A subject may request retreatment with IMP at any time ≥ 12 weeks after their most recent study treatment.

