3.3 Safety Variables

Safety will be assessed throughout the study by evaluating:

- Treatment Emergent Adverse Events (TEAEs)
- Adverse events of special interest (AESI)

- Adverse events (AEs) related to toxin spread
- AEs related to hypersensitivity
- Other protocol defined TEAEs
 - Urinary Tract Infections (UTI)
- Vital signs (heart rate, respiratory rate, blood pressure and body temperature)
- Laboratory blood parameters (haematology and serum chemistry)
- Laboratory urine parameters (laboratory urinalysis/microscopy, culture and sensitivity)
- Development of BTX-A antibodies (neutralizing)
- Usage of concomitant medications and therapies.

Timepoints for safety evaluations are detailed in [Appendix V](#).

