7.6.3 Primary Efficacy Analysis

The primary efficacy endpoint is mean change in the weekly number of UI episodes from study baseline to Week 6 after the first treatment. Seven-day bladder diaries that contain data recorded on at least 5 days will be included in the analysis.

As all subjects should have visits up to and including week 12, but thereafter visits are dependent on whether the subject receives retreatment, statistical testing between treatment

Statistical Analysis Plan

Version: Final v1.0

September-2018

Ipsen Protocol No. D-FR-52120-223

000000146513

Date of Issue: 21-

Covance Study ID:

groups will be performed only up to Week 12, inclusive. Descriptive statistics table will present any timepoint.

Weekly number of UI episodes and the mean change from study baseline will be presented for the DBPC Cycle. The mixed model repeated measures (MMRM) analysis will be conducted with the change of the weekly number of UI episodes from study baseline as response variable. Fixed effect variables include treatment group, visit (Week 2, Week 6 and Week 12), treatment-by-visit interaction, stratification variables [the aetiology of NDO and prior intradetrusor BTX-A usage for UI] and study baseline value of weekly number of UI episodes. Random effect will include the subject effect. An unstructured covariance matrix will be specified in the mixed model to account for within subject correlation. If model fails to converge, the structure of first order autoregressive AR (1), compound symmetry (CS) or variance components (VC) will be used.

The least square means (LSMEANS) of the change of weekly number of UI at each visit in each group with standard error, the difference of mean between the two treatment groups at each visit, the 95% CI of the difference and the p-value for treatment group will be presented. The comparison of main interest will be treatment difference at Week 6.

The SAS codes of MMRM for reference are below.

CCI
[Redacted SAS code]

The validity of the model assumptions of normality will be investigated using residual plots. The LS means of change from study baseline for weekly UI in the DBPC and Dysport Cycles will be presented in line plots by treatment groups.

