Statistical Analysis Plan

Version: Final v1.0

September-2018

Ipsen Protocol No. D-FR-52120-223

000000146513

Date of Issue: 21-

Covance Study ID:

-
- any UTI TEAEs
 - UTI TEAEs leading to withdrawal
 - serious UTI TEAEs
 - TEAE leading to death

In view of the anticipated difference in duration of the Dysport and placebo treatment cycles, this overview table will also be provided including only TEAEs occurring up to 12 weeks after first IMP treatment administration.

A similar overview table will be produced for the number and percentage of subjects with at least one of the following events occurred pre-treatment for randomised subjects. The number of occurrences of the following events will be presented as well.

- any AE
 - Intensity of AE (mild, moderate, severe)
- any SAE
 - any SAEs leading to withdrawal
- AE leading to death

TEAEs will be summarised overall, for DPBC cycle, and Dysport Cycles with the number and percentage of subjects with TEAEs presented by primary SOC and PT. In addition, this table will be provided including only TEAEs occurring any time after first dose of IMP until up to 12 weeks after first IMP treatment administration. This will also be summarised by aetiology of NDO.

For AESIs, summary tables may also be produced following medical review of available information.

The same summaries for overall, for DBPC Cycle, and Dysport Cycles with the number and percentage of subjects with TEAEs presented by primary SOC and PT will be presented for serious TEAEs, IMP-related TEAEs, TEAEs leading to withdrawal, TEAEs of special interest, and other protocol defined TEAEs. TEAEs with PTs observed in $\geq 1\%$, $\geq 2\%$, and $\geq 5\%$ of subjects and IMP-related TEAEs with PTs observed in $\geq 1\%$, $\geq 2\%$, and $\geq 5\%$ of subjects will be summarised as well.

Additionally, TEAEs will be tabulated by decreasing overall PT frequency and intensity in each SOC and PT category.

The above will also be presented for SAEs.

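### SAP 7.4.3 tabulates concomitant medication use by arm over whole DBPC Cycles of unequal length, without the 12-week version that SAP 7.7.1 gives to adverse events

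*SAP*

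**What the plan says.** SAP 3.3 lists "Usage of concomitant medications and therapies" among the safety variables. Protocol 3.2.3 does the same, and Protocol 9.4.7 places the summary by treatment group under the safety evaluation.

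SAP 7.4.3 sets the statistic: medications "will be summarised by treatment group and overall with the number and percentage of subjects, by therapeutic class" and preferred term. It sets the window as well: "The concomitant medications and therapies will be summarised separately for the DBPC Cycle and by Dysport Cycle (Dysport Cycle 1, 2, etc". A drug counts as concomitant if it starts on or after the date of the first injection, or if it started earlier and was still being taken then. The section gives no upper time limit. SAP 7.1 fixes the denominator: "The denominator for percentage calculations will be the number of subjects in the analysis population for the designated treatment cycles". That is a count of subjects, not of time.

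Cycle length depends on the subject. SAP 2.2 says "A subject may request retreatment with IMP at any time ≥ 12 weeks after their most recent study treatment". SAP 7.6.3 draws the consequence for efficacy, "As all subjects should have visits up to and including week 12, but thereafter visits are dependent on whether the subject receives retreatment", and limits testing between arms to Week 12. SAP 7.7.1 draws the same consequence for adverse events: "In view of the anticipated difference in duration of the Dysport and placebo treatment cycles, this overview table will also be provided", restricted to TEAEs in the first 12 weeks. The table by system organ class and preferred term gets the same restricted version. The readable text of SAP 7.4.3 has no equivalent.

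**The concern.** A percentage of subjects with at least one new drug start grows with time observed. If one arm is watched for longer, its percentage is higher even when the drugs are started at the same rate. The SAP recognises this and corrects for it in one set of descriptive safety tables, but not in another that covers a listed safety variable over the same cycle.

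Two readings are exposed. Non-prophylactic antibiotic use would naturally be read next to the urinary tract infection (UTI) TEAEs, yet one would come from a whole-cycle table and the other also from a 12-week table, so the two could appear to disagree only because of their windows. For NDO medication, Protocol 6.4.1 requires stability for at least 12 weeks after the first injection and does not treat later changes as deviations. A whole-cycle percentage mixes early starts, which bear on the Week 6 result, with later permitted ones.

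**Working it through.** The documents state no figure on this point, so there is none to reproduce. The calculation below only illustrates how the mechanism works.

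**Inputs from the documents**
- Statistic: percentage of subjects by arm (SAP 7.4.3), with subjects as denominator (SAP 7.1).
- Window: the whole DBPC Cycle (SAP 7.4.3), which can end by retreatment from 12 weeks onward (SAP 2.2).
- Unequal cycle lengths expected: SAP 7.7.1, with no figure.

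**Assumed inputs, not in the documents**
- The rate r of new starts is constant and equal in both arms: 0.5, 1 or 2 per person-year.
- Placebo cycles last 14 or 20 weeks; Dysport cycles last 24, 36 or 52 weeks.

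**Step 1: no users at baseline.** P(at least one new start in T weeks) = 1 − exp(−r × T/52).

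For r = 1:
- 14 weeks: 1 − exp(−14/52) = 23.6%
- 36 weeks: 1 − exp(−36/52) = 50.0%

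| r per year | Placebo weeks | Dysport weeks | Placebo % | Dysport % | Gap (points) |
|---|---|---|---|---|---|
| 1 | 14 | 24 | 23.6 | 37.0 | 13.4 |
| 1 | 14 | 36 | 23.6 | 50.0 | 26.4 |
| 1 | 14 | 52 | 23.6 | 63.2 | 39.6 |
| 1 | 20 | 36 | 31.9 | 50.0 | 18.0 |
| 0.5 | 14 | 36 | 12.6 | 29.3 | 16.7 |
| 2 | 14 | 36 | 41.6 | 75.0 | 33.3 |

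Gaps are computed before rounding.

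**Step 2: some users at baseline.** A subject already taking the drug is counted whatever the cycle length. With baseline share c, the percentage is c + (1 − c) × [1 − exp(−r × T/52)], so the gap is multiplied by (1 − c). For r = 1 and 14 vs 36 weeks, the gap at c = 0 is 26.35 points to two decimals:
- c = 30%: 0.7 × 26.35 = 18.4 points
- c = 50%: 0.5 × 26.35 = 13.2 points
- c = 90%: 0.1 × 26.35 = 2.6 points
- c = 100%: 0 points

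**Step 3: both arms cut at 12 weeks.** With T = 12 in each arm, the percentage is 10.9%, 20.6% and 37.0% at r = 0.5, 1 and 2. Under equal rates the gap is zero in every case.

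**The case against.** The strongest objection concerns antibiotics. A reader might infer that longer Dysport cycles are bound to show more antibiotic use. The documents do not support that. Protocol 6.2.1 requires prophylactic antibiotics for all subjects, and a course still running at the first injection counts as concomitant under SAP 7.4.3. The SAP does not say that prophylaxis is left out of the general table. If it stays in, the antibiotic class may be near 100% in every arm, which is the c = 100% case above. This stands: the effect then shows only in non-prophylactic use or by preferred term.

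Further points that stand:
- The prophylactic-antibiotic table is tied to fixed procedures (initial treatment, retreatment, urodynamics), so extra weeks in a cycle add little to it.
- SAP 7.4.3 states no cycle for the surgical-procedure table, so a whole-cycle comparison there would be an inference.
- A reader might infer that the UTI question given in Protocol 1.7 as a reason for placebo goes unanswered on equal time. It does not: UTI TEAEs are in the overview table that SAP 7.7.1 repeats for the first 12 weeks.
- Early changes in NDO medication are not hidden. They would be protocol deviations, and SAP 7.3 lists all deviations.
- The protocol synopsis plans no inferential comparison of safety outcomes, so no test is biased.

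Two points carry less weight. SAP 7.6.6.4 shows time between treatments by arm with Kaplan-Meier curves, so the imbalance can be seen, but seeing it does not correct the percentages. SAP 7.5 reports exposure over the whole study, not person-time within the DBPC Cycle. Redacted SAP material might hold a 12-week medication table; that cannot be excluded, but the readable text plans none.

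**Conclusion.** The point holds in limited form. Followed as written, SAP 7.4.3 gives percentages by arm for a listed safety variable over windows that the SAP itself expects to differ in length. For drugs newly started after the first injection, including non-prophylactic antibiotics and NDO medication, those percentages can differ between arms at equal rates.

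The size rests wholly on assumptions. With no baseline users, the combinations of unequal cycles tabulated above give artificial gaps of 13.4 to 39.6 points; baseline use shrinks them, to zero at 100%. The direction also goes a step beyond the text. SAP 7.7.1 anticipates a difference without saying which cycles are longer; longer Dysport cycles are the natural reading, since the plan measures duration of effect by time to retreatment.

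Severity is minor: the tables are descriptive and the main clinical counterpart, UTI TEAEs, already has a 12-week view.

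**What to change.** In SAP 7.4.3 add, for the DBPC Cycle, tables of concomitant medications and of concomitant NDO medications newly started from the first injection up to 12 weeks after it. Separate prophylactic from other antibiotics in these tables. State that the arms are to be read side by side on them, and keep the full-cycle tables as supportive.

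The prophylactic-antibiotic table needs no change. Apply the cut to surgical procedures only if that table is produced by cycle.

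The cost is a short SAP edit and a few extra tables, produced with a date filter on data already collected. The window matches the one in SAP 7.7.1.
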